11.1 SAMPLE SIZE AND POWER

11.2 GENERAL ANALYSIS CONVENTIONS

Statistical analyses will be conducted by TG Therapeutics or its designee. Statistical analysis will be performed on the intent-to-treat (ITT) population for primary efficacy endpoints and the Treated Population for primary and secondary efficacy endpoints and for safety endpoints.

Baseline is defined as the last measurement for a variable prior to the initial dose of study treatment. Hypotheses will be tested at the 5%, two-sided statistical significance level, unless otherwise specified. Efficacy and safety analyses will be performed using SAS® version 9.2 or higher (SAS Institute, Cary, NC), or comparable software.

All data collected on the eCRF will be listed. Routine data listing or tabulation review during the study conduct will be performed to identify missing data, anomalies, outliers, etc. A complete description of data handling rules and planned statistical analyses is detailed in a separate statistical analysis plan (SAP) prior to conducting any planned analysis.

11.3 ANALYSIS POPULATIONS

The intent-to-treat (ITT) population will include all randomized patients. The Treated Population will include all randomized patients who received at least one dose of study medication.

11.4 PATIENT DISPOSITION

The disposition of patients includes the number and percentage of patients for the following categories: patients enrolled, patients in the ITT and Treated Population, and patients discontinued from the study. The reasons for study discontinuation will also be summarized in this table. Only one primary reason for study discontinuation will be reported in the summary. However, all reasons will be presented in the listing.

A listing will present data concerning patient disposition.

11.5 PATIENT DEMOGRAPHICS AND BASELINE CHARACTERISTICS

UTX-IB-301

Baseline demographic and clinical characteristics will be summarized as percentages for categorical variables and as mean, standard deviation, median, minimum and maximum for continuous measures. The analyses of baseline characteristics will be performed for the ITT and Treated Population.

11.6 MEDICAL HISTORY

Medical history will be captured at the Screening visit. Medical history will be coded using MedDRA and will be summarized by MedDRA system organ class and preferred term for the ITT and Treated Population.

11.7 EXTENT OF EXPOSURE

The dose (mg) of study drugs administered, the total number of doses of study drugs, and the duration of treatment (number of study cycles) will be summarized with descriptive statistics. The number and percentage of patients whose dose is modified at any time will be summarized by each type of modification by cycle and overall. The proportion of patients completing each cycle of treatment will be summarized.

11.8 EFFICACY ANALYSES

All patients included in the study should have a baseline tumor assessment within 30 days of Cycle 1/Day 1. Each patient will be assigned one of the following categories: 1) complete response, 2) partial response, 3) stable disease, 4) progressive disease, 5) early death from malignant disease, 6) early death from toxicity, 7) early death because of other cause, or 9) unknown (not assessable, insufficient data).

The primary analyses of efficacy variables that include measures of tumor response (e.g., ORR, CR rate) will involve response as determined by the IRC. Supportive analyses of these variables will involve response as determined by the investigators.

11.9 MISSING VALUE HANDLING PROCEDURES

Missing data will not be imputed, except for missing dates concerning major efficacy or safety parameters. The algorithms for imputation of partial dates vary depending upon the parameter and are presented in the Statistical Analysis Plan.

11.10 STATISTICAL ANALYSES

11.10.1 PRIMARY EFFICACY VARIABLES

The ORR is defined as the proportion of patients with a best overall response of partial response (PR) or complete response (CR). Patients who do not have a tumor response assessment for any reason will be considered non-responders and will be included in the denominator when calculating the ORR. For the ITT analysis, for each treatment group, the number of patients achieving a response will be divided by the total of patients in the ITT population to yield the proportion responding.

UTX-IB-301

The primary efficacy variable (i.e. ORR) will be analyzed in the ITT population first and then will also be analyzed for the Treated Population.

The ORR will be compared between treatment groups by a Fisher's Exact Test. Testing of ORR will be at the 5%, 2-sided statistical significance level.

ORR will also be analyzed based on Per Protocol patients. Additional sensitivity analyses will also be performed as appropriate.

11.10.2 SECONDARY EFFICACY VARIABLES

11.10.2.1.1 COMPLETE RESPONSE RATE

The CR rate is defined as the proportion of patients with a best overall response of complete response (CR). Patients who do not have a tumor response assessment for any reason will be considered non-responders and will be included in the denominator when calculating the CR rate. For each treatment group, the number of patients achieving a CR will be divided by the total of patients in the Treated Population to yield the proportion responding.

The CR rate will be compared between treatment groups at the 5%, two-sided statistical significance level using the same methodology as that described in Section 11.10.1 found for ORR.

11.10.2.1.2 DURATION OF RESPONSE

The Duration of Response (DOR) is defined as the interval from the first documentation of CR or PR to the earlier of the first documentation of disease progression or death from any cause. The DOR rate will be compared between treatment groups at the 5%, two-sided statistical significance level using an ANOVA model with treatment effect.

11.10.2.1.3 TIME TO RESPONSE

The Time to Response (TTR) is defined as the interval from the start of study drug to the first documentation of CR or PR. The TTR rate will be analyzed via Kaplan-Meier methodology using a stratified Cox regression model with treatment effect and stratification effect to compare the treatment groups to generate the treatment group HR and 95% CI.

11.10.2.1.4 MINIMAL RESIDUAL DISEASE NEGATIVITY RATE

The MRD negativity rate is defined as the proportion of patients who are MRD negative post-baseline. MRD negativity rate is defined as the proportion of the patients in the Treated Population who are MRD negative, excluding any patients who remain on study treatment at the time of the analysis and have a Cycle 1/Day 1 start date less than 6 months from the time of the analyses. For the sake of clarity, the MRD negative analysis will exclude those patients that are too early to evaluate because MRD negativity is only tested for patients on study ≥ 6 months. Patients who drop off study for any reason prior to their 6 month visit will be included in the analysis.

The MRD negativity rate will be compared between treatment groups at the 5%, two-sided statistical significance level using the same methodology as that described in Section 11.10.1 for ORR.

11.10.2.1.5 SAFETY

UTX-IB-301

Safety analyses will be performed on the Treated Population. Safety evaluations will be based on the incidence, intensity, and type of adverse events, as well as on clinically significant changes in the patient's physical examination, vital signs, and clinical laboratory results. Safety variables will be tabulated and presented by study drug actually received.

Because there is no pre-specified safety outcome defined in terms of AEs, clinically relevant laboratory parameters, or vital signs, any formal comparisons between the treatment arms with respect to specific safety parameters will be post-hoc.

11.10.2.1.6 PROGRESSION-FREE SURVIVAL

Progression-free survival is defined as the time from the date of randomization until the date of first documentation of definitive disease progression or date of death from any cause, whichever occurs first. Patients who die without a reported prior progression will be considered to have progressed on the day of their death. Patients who did not progress or are lost to follow-up will be censored at the day of their last tumor response assessment. If no baseline or post-baseline assessment is available, the patient will be censored at the date of randomization. If death or PD occurs after 2 or more consecutive missing tumor response assessments, censoring will occur at the date of the last response assessment prior to the missed assessments. The use of a new anticancer therapy prior to the occurrence of PD will result in censoring at the date of last tumor response assessment prior to initiation of new therapy.

This variable will be analyzed via Kaplan-Meier methodology. The median PFS will be estimated for each arm, however no formal hypothesis testing will be conducted.

UTX-IB-301

12.1 SAFETY ANALYSES

Safety evaluations will be based on the incidence, intensity, and type of adverse events, as well as on clinically significant changes in the patient's physical examination, vital signs, and clinical laboratory results. Safety analyses will be performed using the Treated Population. Safety variables will be tabulated and presented by the dose of ublituximab and/or ibrutinib actually received. Exposure to study treatment and reasons for discontinuation of study treatment will also be tabulated.

The number of dose reductions of ibrutinib due to toxicity (adverse events) in each treatment arm will be compared.

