Treatment-emergent AEs through 30 days after last dose of study treatment will be summarized by Medical Dictionary for Regulatory Activities (MedDRA™), Version 13.1 (or higher), System Organ Class and preferred term. The incidences and percentages of patients experiencing each AE preferred term will be summarized with descriptive statistics. The severity of AEs will also be summarized by National Cancer Institute Common Terminology Criteria for Adverse Events (NCI-CTCAE), Version 4.0 (or higher) grade and by causality (relationship to study treatment). Grade 3 and 4 AEs, SAEs, and AEs leading to withdrawal, dose modification, or treatment discontinuation will also be summarized by preferred term. Laboratory results will be classified according to NCI-CTCAE, Version 4.0 (or higher). Laboratory results not corresponding to an NCI-CTCAE term will not be graded. Incidences of laboratory abnormalities will be summarized with descriptive statistics. Vital signs and physical examination results will be summarized with descriptive statistics.

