8.4.2 DOSE DELAYS/MODIFICATIONS: IBRUTINIB

Interrupt ibrutinib therapy for any Grade 3 or greater non-hematological, Grade 3 or greater neutropenia with infection or fever, or Grade 4 hematological toxicities. Once the symptoms of the toxicity have resolved to Grade 1 or baseline (recovery), ibrutinib therapy may be reinitiated at the starting dose. If the toxicity reoccurs, reduce dose by one capsule (140 mg per day). A second reduction of dose by 140 mg may be considered as needed. If these toxicities persist or recur following two dose reductions, discontinue ibrutinib.

Once reduced, the dose of ibrutinib may not be re-escalated. If further evaluation of the toxicity reveals the event was not treatment related, this must be recorded in the medical record and dose re-escalation to the next higher dose level may be considered at the discretion of the investigator.

For adverse events related to ibrutinib, refer to Table 3: Study Drug Dose Reduction Levels: Ibrutinib provided below. Please refer to the FDA approved prescribing information for all safety updates and dose modifications for ibrutinib. For the most up to date information please see www.imbruvica.com.

TABLE 3: STUDY DRUG DOSE REDUCTION LEVELS: IBRUTINIB

Toxicity Occurrence	CLL Dose Modification After Recovery (Starting Dose = 420 mg)	
First	Restart at 420 mg daily	
Second	Restart at 280 mg daily	
Third	Restart at 140 mg daily	
Fourth	Discontinue ibrutinib	

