7 SAFETY ANALYSES

Safety analyses will be performed on the Treated Population. Safety evaluations will be based on the incidence, intensity, and type of adverse events, as well as on clinically significant changes in the patient's physical examination, vital signs, and clinical laboratory results. Safety variables will be tabulated and presented by study drug actually received.

Because there is no pre-specified safety outcome defined in terms of AEs, clinically relevant laboratory parameters, or vital signs, any formal comparisons between the treatment arms with respect to specific safety parameters will be post-hoc.

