8 ADVERSE EVENTS

Each AE and SAE term recorded on the case report forms (CRFs) will be mapped to a preferred term (PT) using the MedDRA dictionary. The investigator will classify the severity of AEs and SAEs using the NCI CTCAE v4.0 and will assess the relationship of each event to study treatment.

All AEs and SAEs occurring on study will be listed by treatment drug, center, and patient. The frequency and percentages of patients with treatment-emergent adverse events (TEAEs) will be tabulated by system organ class (SOC) and PT, where treatment-emergent is defined as any AE that;

- occurs on or after Cycle 1/Day 1 and through the end of the study or, if serious, up through 30 days after the last dose of study treatment;
- is present before Cycle 1/Day 1 but worsens in intensity or the investigator subsequently considers treatment-related.

For the purpose of calculating treatment emergence and inclusion in summary tables, incomplete onset dates will be imputed as detailed in Appendix A – Imputation Rules for Missing Data. Summaries will display incidence by study drug received and total incidence, and PTs within each SOC will appear in decreasing order of total incidence as well as in alphabetical order. At each level of summarization, a patient will be counted only once for each AE, SOC, or PT experienced within that level.

Related TEAEs, serious TEAEs, Grade 3 or higher TEAEs, related serious TEAEs, related Grade 3 or higher TEAEs, and TEAEs resulting in discontinuation of study treatment will be similarly summarized. Summaries of TEAEs by relationship to the study treatment will also be prepared.

At each level of summarization, a patient will be counted only once for each AE, SOC, or PT experienced within that level. In the summation for AE severity, within each level of AE, SOC, or PT experienced, the one with the highest severity will be included. In the summation for AE's relationship to the study drug, within each level of AE, SOC, or PT experienced, the one with the closest relationship to the study drug will be included.

AEs will be summarized for the treatment that the patient last receives prior to the occurrence of the AEs.

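### Protocol 12.1 groups safety by dose received and compares a bare count of ibrutinib reductions, and the readable SAP carries over none of the protocol's dose-modification summaries

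*Protocol*

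**What the plan says.** **Grouping of safety data.** Protocol 12.1: "Safety variables will be tabulated and presented by the dose of ublituximab and/or ibrutinib actually received". Protocol 11.10.2.1.5, and SAP 7 in the same words: "Safety variables will be tabulated and presented by study drug actually received". The protocol synopsis uses the regimen actually received. SAP 4 fixes two columns in every table, one per regimen. SAP 8 adds that each AE is summarised under the treatment last received before it occurred.

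**Dose modification in the protocol.** Three outputs are planned:
- Section 12.1: "The number of dose reductions of ibrutinib due to toxicity (adverse events) in each treatment arm will be compared".
- Section 11.7: "The number and percentage of patients whose dose is modified at any time will be summarized by each type of modification by cycle and overall".
- Synopsis, Safety Analyses: "AEs leading to withdrawal, dose modification, or treatment discontinuation will also be summarized by preferred term".

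**Dose modification in the SAP.** SAP 5.7 lists patients dosed, duration of exposure, number of doses and cumulative dose, for each drug and by arm. SAP 8 says "TEAEs resulting in discontinuation of study treatment will be similarly summarized". The readable text has no summary of reductions, interruptions or AEs leading to dose modification. SAP 7 adds that "any formal comparisons between the treatment arms with respect to specific safety parameters will be post-hoc".

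**How ibrutinib dose changes.** In Protocol 8.4.2 and Table 3 the first qualifying toxicity leads to a restart at 420 mg, the second at 280 mg, the third at 140 mg, and the fourth to discontinuation: "If these toxicities persist or recur following two dose reductions, discontinue ibrutinib". Protocol 8.4.1 allows no ublituximab reduction, and lets an Arm A patient stop one drug and continue the other.

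**The concern.** Both arms take ibrutinib at the same starting dose, so whether adding ublituximab costs ibrutinib delivery is part of the secondary safety objective and helps in reading ORR and PFS. There are three weaknesses.

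1. Ibrutinib dose level after randomisation is partly a consequence of toxicity. A table that splits patients by dose received can show more toxicity at lower doses when dose has no effect.
2. The number of reductions per arm is a legitimate outcome, but it competes with stopping. A patient who stops ibrutinib for toxicity contributes no later reduction, so an arm with much more stopping can show fewer reductions.
3. Protocol 11.2 leaves the complete description of the analyses to the SAP. SAP 2 says the SAP is based on the 31 July 2017 protocol, yet the three dose-modification outputs are absent from its readable text and nothing explains why. Cumulative dose alone cannot separate reduction, interruption, stopping and short follow-up.

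**Working it through.** The documents give no safety rates, so there is no figure of the plan's own to reproduce. All rates below are assumptions. The Table 3 steps and about 60 patients per arm (about 120 randomised 1:1) come from the documents.

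**A. Grouping by dose received, with no true effect of dose.**

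*Columns by lowest dose ever received.* Let qualifying toxicities per patient be Poisson with mean m, and let only toxicity change the dose. Then:
- overall incidence = 1 − e^(−m);
- incidence in the full-dose column (0 or 1 event) = m/(1+m);
- share of patients reduced = 1 − e^(−m)(1+m).

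| m | Overall | Full-dose column | Share reduced |
|---|---|---|---|
| 0.3 | 25.9% | 23.1% | 3.7% |
| 0.6 | 45.1% | 37.5% | 12.2% |
| 1.0 | 63.2% | 50.0% | 26.4% |

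In this model the reduced-dose column is at 100% by construction.

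*Columns by dose at the time of the event.* I simulated the Table 3 steps over 12 cycles, with a toxicity hazard of 0.05 per cycle and 1% other discontinuation per cycle. Events per 100 patient-cycles at 420, 280 and 140 mg are 4.9, 4.9 and 4.8 if patients are alike. They are 4.5, 10.3 and 13.4 if susceptibility varies (gamma, shape 1). So the distortion depends on how the columns are built, which 12.1 does not say.

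**B. The reduction count.** Let N be Poisson with mean λT, T = 1.5 years, and let each toxicity end ibrutinib with probability s (the fourth always does). Per patient:
- reductions = (1−s)²·P(N≥2) + (1−s)³·P(N≥3);
- permanent stop = 1 − Σ(k=0..3) (1−s)^k·P(N=k);
- reduction or stop = 1 − P(N=0) − (1−s)·P(N=1);
- years on ibrutinib = (1/λ)·Σ(k=0..3) (1−s)^k·P(N≥k+1).

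Arm A: λ = 0.8 per year, s = 0.4, λT = 1.2, P(N≥2) = 0.3374, P(N≥3) = 0.1205. Reductions = 0.36 × 0.3374 + 0.216 × 0.1205 = 0.1475, or 8.8 per 60.

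Arm B: λ = 0.6 per year, s = 0.1, λT = 0.9, P(N≥2) = 0.2275, P(N≥3) = 0.0629. Reductions = 0.81 × 0.2275 + 0.729 × 0.0629 = 0.2301, or 13.8 per 60.

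| Per 60 patients | Arm A | Arm B |
|---|---|---|
| Any toxicity, 1 − e^(−λT) | 70% | 59% |
| Reductions | 8.8 | 13.8 |
| Patients with at least one reduction, 60(1−s)²·P(N≥2) | 7.3 | 11.1 |
| Patient-years on ibrutinib | 71.4 | 85.9 |
| Reductions per patient-year | 0.124 | 0.161 |
| Permanent stops | 23.1 | 5.7 |
| Reduction or stop | 28.9 | 15.8 |

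The count, the number of patients reduced and the rate per patient-year all favour the more toxic arm. Stops and the composite do not.

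**Sensitivity.** Keeping Arm B at 13.8 and varying s in Arm A:

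| s in Arm A | 10% | 15% | 20% | 25% | 30% | 40% |
|---|---|---|---|---|---|---|
| Reductions per 60 | 21.7 | 19.1 | 16.7 | 14.4 | 12.4 | 8.8 |

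The order reverses between 25% and 30% (at about 27%).

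**C. Protocol against SAP.**

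| Output | Protocol | Readable SAP |
|---|---|---|
| Patients with dose modified, by type and cycle | 11.7 | absent |
| Ibrutinib reductions compared by arm | 12.1 | absent |
| AEs leading to dose modification | synopsis | absent |
| AEs leading to discontinuation | synopsis, 12.4 | SAP 8 |
| Duration and amount of dosing | 11.7 | SAP 5.7 |

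The blacked-out SAP parts appear to lie among the objectives and in the efficacy chapter, so they are unlikely to hold these outputs.

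**The case against.** The strongest reply is that the SAP already settles the grouping. With two regimen columns, a by-dose table would never be made, and because ublituximab cannot be reduced, the 12.1 wording can be read as loose as-treated language. That stands: the by-dose bias arises only if 12.1 is followed literally.

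A reader might infer that every patient in a reduced-dose column has had two toxicities. The documents do not support this. Protocol 8.2.2 and 9.2 refer to the prescribing information for dosing with a moderate CYP3A inhibitor or inducer, 9.2.1 does the same for dose modification in atrial fibrillation, and 8.4.2 allows re-escalation if the event proves unrelated. The 100% in the working belongs to a model in which only toxicity changes the dose and columns follow the lowest dose.

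A reader might also infer that more stopping always means fewer reductions. It does not: up to 25% stopping per toxicity in Arm A, the count points the right way. Nor does dividing by time on ibrutinib cure the reversed case.

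Finally, a reader might infer that the toxicity cost of ublituximab would go unreported. That is too strong. SAP 5.7 and 8 give exposure duration, number of doses, cumulative dose, and related, serious, Grade 3 or higher and discontinuation TEAEs. In the reversed example the stops, 23.1 against 5.7 per 60, reveal the harm, and the SAP's summary of TEAEs leading to discontinuation should capture such stops.

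What the reply leaves standing is the wording conflict, the missing context for the count, and three planned outputs without a place in the readable SAP.

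**Conclusion.** The point holds in a limited form. Protocol 12.1 conflicts with 11.10.2.1.5, the synopsis and SAP 4 and 7 on how safety is grouped; literal use would condition on a post-randomisation outcome. The bare reduction count can understate toxicity in an arm with much more discontinuation: 8.8 against 13.8 per 60 in the illustration, although any toxicity is 70% against 59%. That reversal rests on assumed rates and needs Arm A to stop for roughly 30% or more of toxicities against 10% in Arm B. The firmest part needs no assumption: the protocol plans three dose-modification outputs and the readable SAP contains none.

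A related rule also needs settling. SAP 8 assigns AEs to the treatment last received, and an Arm A patient may stop ublituximab and stay on ibrutinib. That patient's later AEs could be counted under ibrutinib alone, which does not fit a regimen column fixed per patient. The consequence is limited to descriptive safety reporting; the primary ORR test is unaffected.

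**What to change.** 1. In Protocol 12.1, replace grouping by dose with the as-treated regimen, fixed per patient, to match 11.10.2.1.5, the synopsis and SAP 4 and 7.
2. Reconcile the last-treatment-received rule in SAP 8 with those fixed columns.
3. In SAP 5.7, add a descriptive table by arm with n and % of patients having a toxicity-driven ibrutinib interruption, reduction, permanent discontinuation, and the composite of reduction or discontinuation, side by side with time on ibrutinib. Ibrutinib dose intensity is optional. Let this table replace the bare count in 12.1, and do not rely on reductions per patient-year alone. Keep the breakdown by type and cycle that 11.7 promises.
4. In SAP 8, add TEAEs leading to dose modification by preferred term.

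The cost is wording in both documents and two or three extra descriptive tables. They should need no new data: Protocol 8.2.1.3 and 8.2.2 already put ublituximab doses and missed ibrutinib doses on record, and AEs go on the eCRF. These are analysis changes only; nothing here bears on the dosing rules themselves.
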